3.2 Secondary Objective

1. To preliminarily assess the therapeutic response of [177Lu]Lu-TEFAPI-06 in patients with FAP-high expressing tumors.

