7.2 Efficacy Assessment (Follow-up)

Timeline: Baseline (pre-treatment) and 1 month post-treatment.

Modality: [18F]-FAPI PET/CT.

Biological Markers: Tumor-specific serum markers will be measured at baseline and follow-up.

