8. STATISTICAL ANALYSIS PLAN (SAP)

8.1 General Considerations

This is a small-sample exploratory study (N=5). The statistical analysis will be primarily descriptive. No formal sample size calculation based on power analysis was performed due to the pilot nature of the study.

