8.4 Efficacy Analysis

Primary Endpoint (Imaging): Comparison of Standardized Uptake Values (SUV_{max} and SUV_{mean}) of the primary tumor and representative metastatic lesions between baseline and 1-month post-treatment [18F]-FAPI PET/CT scans.

Background Reference: Mean SUV of normal liver tissue.

Secondary Endpoint (Biomarkers): Comparison of serum tumor marker levels pre- and post-treatment.

Statistical Test: Continuous variables (SUV, biomarker levels) will be tested for significant changes using the Paired t-test (if normally distributed) or Wilcoxon signed-rank test (if non-normally distributed).

A P-value < 0.05 will be considered statistically significant.

Data will be presented as Mean \pm SD or Median (Range).

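### Section 8.4 assesses therapeutic response in five patients only through group summaries and a group test at P<0.05; no per-patient change or response count is planned

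*Combined protocol and SAP*

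**What the plan says.** Section 3.2 states the secondary objective as "To preliminarily assess the therapeutic response of [177Lu]Lu-TEFAPI-06 in patients with FAP-high expressing tumors". Section 8.4 is the only place that turns this into an analysis. It compares SUVmax and SUVmean "of the primary tumor and representative metastatic lesions between baseline and 1-month post-treatment [18F]-FAPI PET/CT scans" and compares serum markers before and after treatment. These variables "will be tested for significant changes using the Paired t-test (if normally distributed) or Wilcoxon signed-rank test (if non-normally distributed". The decision line follows: "A P-value < 0.05 will be considered statistically significant". Results are to be shown as mean with SD or median with range.

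Section 8.1 gives the context. There are five patients, "The statistical analysis will be primarily descriptive", and "No formal sample size calculation based on power analysis was performed due to the pilot nature of the study". Section 5.1 requires metastatic disease and high FAP uptake on PET/CT but does not restrict histology. Section 7.2 adds that "Tumor-specific serum markers will be measured at baseline and follow-up", so the marker itself may differ from patient to patient.

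No section defines response in an individual patient, sets a change threshold, plans a responder count, or plans a listing of each patient's paired values. Section 8.4 also does not say whether the unit of analysis is the patient or the lesion, or whether the test is one- or two-sided.

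**The concern.** The objective asks whether patients respond; the analysis asks whether the average or typical patient changed. When histology is open, uneven response is foreseeable, and the two questions can then have different answers. A paired t-test compares the mean change with the spread of changes between patients. One large response raises both, so the test gains nothing from it, whereas a modest change shared by all five patients has little spread and can be significant.

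Section 8.4 offers P<0.05 as its only criterion for a change. A report that follows it could therefore state that there was no significant change when one patient's tumor uptake fell sharply. In a first exploratory study of five patients, that individual result is what a later trial would most want to know. The same rule could also give a significant result when no patient changed by more than two scans of an untreated tumor might differ.

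**Working it through.** The documents state no effect size, power or variability, so there is no planned figure to reproduce. What can be checked is how the planned tests behave at n=5.

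**Inputs from the documents:** n=5 (8.1); paired t-test or Wilcoxon signed-rank test, threshold 0.05 (8.4).

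**Assumptions:** one value per patient; two-sided testing; all change values, SDs and baseline SUVs below are illustrative.

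**1. What the t-test requires.** t = mean/(SD/√5) with 4 df and critical value 2.776. Significance needs |mean|/SD > 2.776/√5 = 1.24, which is the same as SD below 1/1.24 ≈ 0.8 of the mean change.

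**2. One responder, four unchanged.** Let the changes be (D, 0, 0, 0, 0).
- Mean = D/5.
- Sum of squared deviations = D² − 5(D/5)² = 4D²/5, so SD = √(D²/5) = D/√5.
- SE = (D/√5)/√5 = D/5, so |t| = 1 and P = 0.374 for any D.

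With some noise in the others, take changes of −60, +1, −2, +3, −4%: mean −12.4, SD 26.7, SE 26.7/√5 = 12.0, t = −1.04, P = 0.36. A Shapiro-Wilk check on these values gives P = 0.003 (the plan names no normality test), so they would probably go to Wilcoxon, where exact P = 0.44. In simulation, with one patient at −50% and four at zero with noise SD 5, 10 or 15 points, the t-test was significant in 0.0%, 0.4% and 1.9% of trials.

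**3. The Wilcoxon floor.** With n patients the smallest exact two-sided P is 2/2ⁿ: 2/32 = 0.0625 at n=5, and 2/16 = 0.125 if one patient has no 1-month value. Five falls out of five are not significant. Two readings avoid this floor: a one-sided exact test (1/32 = 0.031), and the large-sample approximation without continuity correction (z = 7.5/√13.75 = 2.02, P = 0.043). The plan specifies neither.

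**4. A small consistent shift.** Changes of −3, −5, −7, −8, −2%: mean −5.0, SD 2.55, ratio 0.51, t = −4.39, P = 0.012. Wilcoxon on the same values gives 0.0625. On raw SUV, with assumed baselines 12, 8, 15, 10, 6, the t-test gives P = 0.031. The result depends on the spread: for a true mean of −5%, the chance of a significant t-test is 98%, 56% or 14% when the SD of change is 2, 4 or 10 points.

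**5. How often significance comes with no patient beyond scan repeatability.** Assume a repeatability limit of 20% or 30%, read as 1.96 × the SD of change, so the SD is 10.2 or 15.3 points. With a true mean change of −14%, the t-test was significant with no patient beyond the limit in about 11% and 14% of simulated trials.

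**6. What a count would add.** Exact 95% CIs: 0/5, 0 to 52.2%; 1/5, 0.5 to 71.6%; 2/5, 5.3 to 85.3%; 5/5, 47.8 to 100%.

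**The case against.** The best defense is that the study presents itself as exploratory and mainly descriptive, that response is a secondary objective to be assessed preliminarily, and that no decision is tied to the P-value. All of that is true and limits the stakes. It does not remove the point, because 8.4 still adds a significance rule and offers no other way to judge a change.

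A reader might infer that 8.4 reports nothing but a mean, so that a clear responder simply disappears. The text does not support that. A skewed set of changes would probably go to Wilcoxon and the median with range, and a range of changes would show the extreme patient. However, 8.4 speaks of SUV and marker levels and does not say that changes are summarized. In step 4's assumed baselines, with the −60% fall in the patient starting at 12, the range of SUV is 6 to 15 at baseline and 4.8 to 14.7 at one month, which does not reveal the responder.

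A reader might also infer that a trivial uniform shift would routinely be called significant. That too goes beyond the documents: it cannot happen with the exact two-sided Wilcoxon test, and on the t-test it requires a spread of changes that is small relative to the mean. A consistent fall in all five patients may also be a real group effect.

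Two further limits stand. If lesions rather than patients were tested, n could exceed 5 and the figures above would change, but lesions from one patient would then be treated as independent. And individual listings could be added at reporting without altering the plan; a threshold chosen at that stage, however, could be fitted to the data.

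**Conclusion.** The point holds in this form: the only planned assessment of response is a group summary with a group test, and with one value per patient that test cannot answer the stated objective at n=5. A lone responder among unchanged patients leaves the t-test at P≈0.37; the exact two-sided Wilcoxon test has a floor of 0.0625; a small consistent shift can be significant only on the t-test, when the SD of change is below about 0.8 of the mean. The first and third results are arithmetic for a two-sided test at n=5, and the second also needs the exact version of the test. How likely each situation is rests on assumed changes and SDs, since the documents give none.

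It would go too far to say that five different cancers will be enrolled, since open histology only makes this possible, or that a go/no-go decision will rest on the P-value, since none is described. The change is worth making, in proportion to a secondary objective.

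**What to change.** In section 8.4, make the main response output a per-patient table: tumor type, administered activity, and baseline, 1-month and percentage change in SUV, with one value per patient by a stated rule. A patient without a 1-month scan stays in the table as not evaluable.

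Report how many of the 5 treated patients have a fall, and how many a rise, beyond a measurement-repeatability limit written into the SAP before the first 1-month scan, each with an exact 95% CI. Give the group mean change with its 95% CI as a supporting summary. Label any P-value descriptive and state that it is not the criterion for response.

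The cost is one table and a few sentences, with no new scans or patients. The drawbacks are real but manageable. A limit has to be chosen and justified in advance; the documents give no value, and the 20–30% used above is an assumption. The count out of 5 makes a responder visible but estimates the response rate very poorly. Listing five individuals needs the usual care over identifiability.

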1. STUDY SYNOPSIS

Study Phase: Exploratory (Phase 0/I)

Investigational Product:[177Lu]Lu-TEFAPI-06

Indication: fibroblast activation protein (FAP)-high expressing metastatic solid tumors

Methodology: Open-label, single-center, single-arm study

Sample Size: 5 participants

Intervention:Single intravenous injection of approx. 20 MBq/kg [177Lu]Lu-TEFAPI-06.

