4. STUDY DESIGN

This is a prospective, single-center, open-label, exploratory clinical trial.

5 eligible patients will receive a single dose of the investigational drug.

Patients will undergo serial whole-body imaging to assess biodistribution and will be followed up for 1 month to assess safety and efficacy.

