8.2 Analysis Sets

Full Analysis Set (FAS):All participants who received the study drug and have at least one post-baseline efficacy evaluation.

Safety Set (SS):All participants who received the study drug.

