8.6 Handling of Missing Data

Given the small sample size, missing data will not be imputed. Analyses will be performed on observed data only.

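### With five patients, the Wilcoxon branch of Section 8.4, read as exact, two-sided and patient-level, cannot reach its own P < 0.05 rule (minimum 0.0625)

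*Combined protocol and SAP*

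**What the plan says.** Section 8.4 says that SUV and biomarker levels "will be tested for significant changes" by a "Paired t-test (if normally distributed) or Wilcoxon signed-rank test (if non-normally distributed"), and that "A P-value < 0.05 will be considered statistically significant". The SUVs are those of "the primary tumor and representative metastatic lesions", compared between baseline and one month.

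The sample is fixed in Section 1 ("Sample Size: 5 participants") and Section 4 ("5 eligible patients will receive a single dose of the investigational drug"). Section 8.2 limits the efficacy set to treated participants who "have at least one post-baseline efficacy evaluation", and Section 8.6 says that "missing data will not be imputed. Analyses will be performed on observed data only". At patient level there can therefore be five pairs or fewer, never more.

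The plan does not say whether the tests are one- or two-sided, whether the signed-rank P-value is exact or approximate, how normality is judged, or whether the unit is the patient or the lesion. Section 8.1 describes the analysis as mainly descriptive and reports no power calculation.

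**The concern.** A signed-rank test on very few pairs has a coarse set of possible P-values, and its smallest value may lie above the chosen threshold. If so, the plan sends non-normal data to a test that cannot succeed under the plan's own rule, whatever the data show.

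The paired t-test has no such floor. The same uniform fall in five patients could then be called significant or not according to a normality judgement on five numbers and, in the Wilcoxon branch, a software setting. Neither is prespecified.

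What is at stake is limited. Therapeutic response is the secondary objective in Section 3.2 and is to be assessed only preliminarily. The primary objectives in Section 3.1 (safety and dosimetry) and the planned descriptive summaries are unaffected.

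**Working it through.** The plan gives no power, effect size or SD, so it has no figure of its own to reproduce. The check asks what Section 8.4 can deliver.

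**Inputs from the documents.** n = 5 (Sections 1, 4 and 8.1); threshold 0.05 and the two tests (Section 8.4).

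**Assumptions.** Two-sided, because the text names no direction of change. Exact P-value and one pair per patient, because these are the ordinary choices at this sample size; the plan states neither.

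**Step 1: the floor.** Under the null hypothesis each of the 2^n sign patterns is equally likely. The most extreme result, all changes in one direction, has one-sided P = 1/2^n and two-sided P = 2/2^n.

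| Pairs | One-sided minimum | Two-sided minimum |
|---|---|---|
| 3 | 1/8 = 0.125 | 2/8 = 0.25 |
| 4 | 1/16 = 0.0625 | 2/16 = 0.125 |
| 5 | 1/32 = 0.031 | 2/32 = 0.0625 |
| 6 | 1/64 = 0.016 | 2/64 = 0.031 |

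Six pairs are needed for the exact two-sided test to go below 0.05.

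**Step 2: the normal approximation.** With all changes in one direction and no ties, z = (M − μ)/σ, where M = n(n+1)/2, μ = n(n+1)/4 and σ² = n(n+1)(2n+1)/24.
- n = 5: M = 15, μ = 7.5, σ = √13.75 = 3.708. Uncorrected z = 7.5/3.708 = 2.02, P = 0.043. With continuity correction z = 7.0/3.708 = 1.89, P = 0.059.
- n = 4: M = 10, μ = 5, σ = √7.5 = 2.739. P = 0.068 uncorrected and 0.100 corrected.

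At n = 5 the label depends on the continuity setting. At n = 4 both settings miss 0.05.

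**Step 3: the t-test branch.** It reaches P < 0.05 when |mean change|/SD exceeds t(0.975, 4)/√5 = 2.776/2.236 = 1.242, which is possible with five patients.

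**Step 4: an illustration with invented falls of 20, 22, 24, 26 and 48 units.** The mean is 28 and the SD 11.40, so the ratio is 2.46 and t = 28/(11.40/√5) = 5.49, P = 0.005. Shapiro-Wilk gives P = 0.022, which would route the data to the signed-rank test, where P = 0.0625.

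**Step 5: how often the switch matters.** The plan names no normality method, so Shapiro-Wilk at 0.05 is assumed. For five differences, the Wilcoxon branch is entered in 5% of datasets for normal data, 9% for t with 3 df, 10% to 24% for lognormal data (log-SD 0.5 to 1.0) and 16% for exponential data (40,000 runs each).

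For SUV falls, assume a lognormal baseline, a log-SD of change of 0.2, and tests on absolute differences. Among runs in which all five SUVs fall (40,000 runs per row before that restriction):

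| Baseline log-SD | True fall | Routed to Wilcoxon | t-test P < 0.05 among those routed | Product: label lost by the switch alone |
|---|---|---|---|---|
| 0.3 | 30% | 6.0% | 83.5% | 5.0% |
| 0.3 | 50% | 6.4% | 98.6% | 6.3% |
| 0.5 | 30% | 10.0% | 45.9% | 4.6% |
| 0.5 | 50% | 10.4% | 67.3% | 7.0% |
| 0.8 | 30% | 19.3% | 14.0% | 2.7% |
| 0.8 | 50% | 17.9% | 21.5% | 3.8% |

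A judgement of normality by eye could enter the branch more or less often.

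**Step 6: fewer than five pairs.** One missed follow-up scan leaves four pairs and a floor of 0.125. For serum markers this is a more natural risk: Section 7.2 makes them specific to the tumor, while Section 5.1 admits any metastatic solid tumor, so a given marker may apply to only some patients.

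**The case against.** The strongest objection is that the floor needs three conditions the plan does not state. The absence of a direction supports a two-sided test but says nothing about exactness or unit. Section 8.4 speaks of metastatic lesions in the plural, so lesion-level pairing is a possible reading, and six or more pairs would remove the floor. A one-sided test (0.031) or the uncorrected approximation (0.043) would also remove it at n = 5.

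That stands as a limit on the claim. It does not rescue the plan. Lesion-level pairing would count lesions within a patient as independent, the approximation is unreliable at n = 5, and the plan states no one-sided test.

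Second, the practical effect is small. By the simulations, in 93% to 97% of 5-of-5 falls the switch does not change the label, and those rates rest on assumptions from outside the documents. In the same scenarios the t-test itself misses 0.05 in 0.2% to 46% of 5-of-5 falls, so the small sample and the absolute-difference scale often matter more than the Wilcoxon floor. The illustration was chosen to trigger the switch. All of this is correct and supports a low severity.

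Third, the floor can only withhold a significant label, the analysis is declared mainly descriptive, and nothing in the documents makes a missing one-month scan likely. This is also fair. But a descriptive aim does not cancel a test and a threshold that Section 8.4 still sets.

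Fourth, a t-interval keeps the t-test's normality assumption, and one sentence stating the test type would settle the ambiguity. This stands in part: the interval is useful only as an estimate, and the fix therefore includes the option of keeping the test with its type and floor stated.

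**Conclusion.** The concern holds, as a minor point. On a two-sided, exact, patient-level reading, the Wilcoxon branch of Section 8.4 has a minimum P of 0.0625 with five pairs and 0.125 with four, so it can never satisfy the plan's rule. Given that reading, the result is certain. The reading itself is an inference, because the plan is silent on all three conditions.

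The estimate that the switch alone changes the label in about 3% to 7% of 5-of-5 falls is weaker. It depends on the assumed effects, spreads and normality test.

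The consequence is confined to a significance label on a secondary, preliminary objective, and no stated decision rests on it.

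**What to change.** Amend Section 8.4 as follows.

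1. Delete the normality-based choice of test and the P < 0.05 sentence. This fits the descriptive aim in Section 8.1.
2. Define one value per patient for each measure, so that several lesions in one patient do not count as independent pairs. Primary tumor and metastases may be summarised separately.
3. List every patient's change.
4. Report the mean change with a 95% t-interval, labelled exploratory; log(1-month/baseline) is a reasonable scale. State in advance the smallest number of patients for which an interval will be given, and list rarer markers patient by patient.
5. If a signed-rank P-value is kept, state that it is exact, two-sided, patient-level and exploratory, with a minimum of 0.0625 at n = 5 and 0.125 at n = 4.

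The cost is SAP wording only, plus the loss of a significance label. The intervals will be wide and still assume approximate normality. On the ratio scale the estimate is multiplied and divided by exp(t(0.975, n−1)/√n × log-SD). For an assumed log-SD of 0.2 to 0.5 that factor is 1.28 to 1.86 at n = 5, 1.37 to 2.22 at n = 4 and 1.64 to 3.46 at n = 3. Such an interval excludes no change exactly when a paired t-test on the same scale gives P < 0.05, so it should be read as an estimate and not as a pass/fail rule.

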8.5 Safety Analysis

Adverse Events (AEs): All AEs will be coded and graded according to CTCAE v5.0 (Common Terminology Criteria for Adverse Events).

Tabulation: The number and percentage of patients experiencing AEs will be summarized by system organ class and severity grade.

Laboratory Data: Descriptive statistics will be used to summarize changes in hematology and chemistry values from baseline to post-treatment. Particular attention will be given to renal toxicity and myelosuppression (Grade 3/4 toxicity).

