3. STUDY OBJECTIVES

3.1 Primary Objectives

1. To evaluate the safety and tolerability of [177Lu]Lu-TEFAPI-06 in patients with metastatic solid tumors.
2. To determine the biodistribution and calculate the radiation absorbed dose in normal organs and tumor lesions.

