5.2 Exclusion Criteria

1. Pregnancy or lactation.
2. Severe hepatic or renal dysfunction (e.g., Creatinine > 1.5x ULN; ALT/AST > 3x ULN).
3. Severe hematological suppression (e.g., WBC < 3.0×10⁹/L, Platelets < 75×10⁹/L).
4. Known severe allergy to the drug or its components.

5. Any other condition that the investigator deems unsuitable for participation.

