7.3 Safety Assessment

Vital signs and physical examination.

Laboratory tests: Complete blood count (CBC), Urinalysis, Liver function tests (LFTs), Renal function tests.

12-lead Electrocardiogram (ECG).

Adverse Event (AE) monitoring throughout the study.

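### Section 8.5 summarises laboratory safety as change to an undefined post-treatment value and gives its Grade 3/4 statement no output; a per-participant worst-grade shift table and listing should be added

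*Combined protocol and SAP*

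**What the plan says.** Section 3.1 lists as its first primary objective "To evaluate the safety and tolerability of [177Lu]Lu-TEFAPI-06 in patients with metastatic solid tumors". Section 4 states that "5 eligible patients will receive a single dose of the investigational drug" and that they "will be followed up for 1 month to assess safety and efficacy".

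Section 7.3 names the tests ("Laboratory tests: Complete blood count (CBC), Urinalysis, Liver function tests (LFTs), Renal function tests") without draw times or a number of draws. It also provides for AE monitoring for the whole study.

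Section 8.5 has three relevant elements:
- AEs are graded by CTCAE v5.0 and tabulated as numbers and percentages of patients, by system organ class and grade.
- For laboratory data, "Descriptive statistics will be used to summarize changes in hematology and chemistry values from baseline to post-treatment".
- On severe toxicity, "Particular attention will be given to renal toxicity and myelosuppression (Grade 3/4 toxicity").

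Section 5.2 excludes "Severe hematological suppression", with WBC below 3.0 and platelets below 75 ×10⁹/L as examples. It also excludes severe hepatic or renal dysfunction, with creatinine above 1.5 times ULN and ALT/AST above 3 times ULN as examples. Section 8.6 restricts analyses to observed values.

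**The concern.** Two things are left open in section 8.5. The first is the end point of the laboratory change: neither 8.5 nor 7.3 dates it or says which value is taken when there are several. The second is the output for Grade 3/4 renal and marrow toxicity: the plan promises attention to it but defines no worst value, worst grade, table or listing.

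The question in a first human safety evaluation is how far each participant's counts and renal function fell, and from what starting level. A group change to one chosen occasion does not answer it. A severe value drawn at another time can be left out of the summary, and a change score does not show the grade reached or the grade already present at entry. With five participants, one case is 20 percentage points of the observed rate.

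**Working it through.** The plan states no figure on this point (section 8.1: "No formal sample size calculation based on power analysis was performed due to the pilot nature of the study"), so there is nothing to reproduce. The check compares the sections and then uses illustrations. All post-baseline platelet values, the cut of 50 and the durations below are assumptions. They are not taken from the documents and are not proposed clinical rules.

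**1. What is dated and what has an output**

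| Item | Section | Specified |
|---|---|---|
| Imaging | 7.1 | six time points, 0.5 to 120 hours |
| Efficacy PET/CT | 7.2 | baseline and 1 month |
| Laboratory draws | 7.3 | tests named, no times |
| Laboratory change | 8.5 | end occasion not defined |
| Grade 3/4 renal and marrow toxicity | 8.5 | no output defined |
| AEs | 8.5 | patients by organ class and grade |
| When a laboratory abnormality becomes an AE | – | not stated |

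A change to a single 1-month value would therefore comply with 8.5, even if other draws existed.

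**2. A low value that was drawn but is not the summarised occasion** (platelets ×10⁹/L, assumed)

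| Participant | Baseline | Lowest | 1 month | Change to lowest | Change to 1 month |
|---|---|---|---|---|---|
| 1 | 220 | 190 | 210 | −30 | −10 |
| 2 | 200 | 180 | 195 | −20 | −5 |
| 3 | 240 | 40 | 200 | −200 | −40 |
| 4 | 180 | 165 | 175 | −15 | −5 |
| 5 | 210 | 185 | 205 | −25 | −5 |

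- To 1 month: mean change −65/5 = −13.0, SD 15.2, range −40 to −5; 0/5 below 50.
- To lowest: mean change −290/5 = −58.0, SD 79.6, range −200 to −15; 1/5 below 50. The mean lowest count is 760/5 = 152.

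In the first summary neither the SD nor the range reveals participant 3. In the second the mean level of 152 does not, but the SD, the range and the individual row do.

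**3. A low value that is the summarised occasion**

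One participant falls from 200 to 40 and four are unchanged. The mean change is (40 − 200)/5 = −32, which is −32/200 = −16%. The SD is √[(4 × 32² + 128²)/4] = √5120 = 71.6, and the range is −160 to 0. Here an ordinary descriptive summary exposes the case. The weakness is the undefined occasion and the absence of individual grades more than averaging itself.

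**4. Change is not grade**

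A change of −30 takes a participant from 220 to 190. The same change takes one who enters at 75, the edge of the example limit in 5.2, to 45, which is below the illustrative cut. The change summary treats the two alike. Baseline is subtracted, but the resulting grade and the entry grade are not shown together.

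**5. What comes from sampling, not from the summary**

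If a low lasts w days and falls at random in a 30-day follow-up, one draw catches it with probability w/30: 5/30 = 17% for 5 days, 14/30 = 47% for 14 days. This depends on section 7.3. No summary in 8.5 can recover a value that was never drawn.

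**6. Weight of one case at N = 5**

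The observed rate is 1/5 = 20% (exact 95% interval 0.5% to 72%) against 0/5 = 0% (0 to 52%).

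**The case against.** The strongest reply is that section 8.5 already grades AEs by CTCAE, counts patients by severity and singles out Grade 3/4 renal and marrow toxicity, while 7.3 monitors AEs throughout. A severe fall that is drawn and recorded as an AE is counted per patient and not averaged. That stands, and a reader who infers that the change summary is the only laboratory safety evidence would be wrong. It does not close the gap, because nothing says when a laboratory abnormality is recorded as an AE, and the Grade 3/4 sentence has no output of its own.

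Other parts of the reply also stand:
- Descriptive statistics need not mean the mean alone. Section 8.4 reports mean with SD, or median with range, for efficacy. Step 3 shows that an SD or range would expose a low on the summarised occasion; step 2 shows that it need not when the occasion is a different one.
- A reader might infer that abnormalities present at entry would be counted as drug toxicity. The documents do not support this: 8.5 tabulates AEs, not every laboratory value by grade, and nowhere calls an unchanged entry abnormality an AE. The change from baseline also subtracts the entry value.
- The limits in 5.2 are given as examples, and a further criterion lets the investigator exclude for any other condition. Mildly abnormal entry values are permitted, not certain.
- For five participants a listing shows everything. This is why the listing is part of the fix; the shift table adds a summary of it at little cost.

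**Conclusion.** The point holds for the outputs of section 8.5. The laboratory summary has no defined end occasion, the Grade 3/4 statement has no defined output, and nothing planned shows toxicity grade against the grade at entry. A transient severe value in one of five participants can be missed or obscured; the documents do not show that it will be. In the assumed example, the same data give 0/5 below the cut at 1 month and 1/5 at the lowest value, provided the low value was drawn.

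A reader might go further and attribute to the 8.5 summary the loss of a case when blood is taken only once, at 1 month. That is not supported: a worst-value table built on that one draw would also show 0/5. Section 7.3 is silent on timing and does not contradict 8.5. The silence is missing detail, and the conclusion here does not rest on how often blood will be drawn.

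**What to change.** In section 8.5, for CBC and for renal and liver tests:
- Report each participant's worst post-injection value and worst CTCAE grade, using every scheduled and unscheduled draw.
- Present these in a table of baseline grade by worst post-injection grade. Make this the stated output for Grade 3/4 renal toxicity and myelosuppression.
- List all values for all five participants. The descriptive change summary can remain as a supplement once its occasion is named.

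Leave the definition of an AE as it is. The shift table shows whether a grade was already present at baseline, so no rule on counting only new or higher grades is needed, and clinically relevant worsening within a grade is not dropped.

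Align 7.3 and 8.5 on which draws count as post-treatment; their timing is for the sponsor and investigator to set.

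The cost is SAP wording, one small table and a listing. No extra draws are needed for this change. If the sponsor chose to add draws between 120 hours and 1 month, they would fall outside the visits now dated in 7.1 and 7.2, and that cost would be separate.
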